### 5.2.6 Treatment Compliance

Percent compliance will be calculated for the FAS as follows:

$$\text{Compliance} = \frac{\text{Total number of tablets dispensed} - \text{Total number of tablets returned}}{\text{Planned Total number of tablets to be taken}} \times 100\%$$

Overall compliance with study medication will be summarized using descriptive statistics (median, mean, standard deviation, minimum, maximum, and number of subjects with non-missing data) for each treatment group. Subjects will also be categorized by compliance criteria <50%, ≥50%-<80%, ≥80%-≤100%, >100% - ≤120%, >120% and missing. The maximum of planned total number of tablets to be taken will be 84.

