24. Planned surgery which requires general, spinal or epidural anesthesia that will take place during the study. Planned surgery that requires only local anesthesia and can be undertaken as a day case without inpatient stay postoperatively need not result in exclusion if in the opinion of the investigator this operation does not interfere with study procedures and subject safety.
25. Females who are breastfeeding or pregnant at Screening or Baseline (as documented by a positive beta-human chorionic gonadotropin [β -hCG] (or human chorionic gonadotropin [hCG] test) with a minimum sensitivity of 25 IU/L or equivalent units of β -hCG or hCG). A separate baseline assessment is required if a negative screening pregnancy test was obtained more than 72 hours before the first dose of study drug.
26. Females of childbearing potential.
(NOTE: All females will be considered to be of childbearing potential unless they are postmenopausal [amenorrheic for at least 12 consecutive months, in the appropriate age group, and without other known or suspected cause] or have been sterilized surgically [ie, bilateral tubal ligation, total hysterectomy, or bilateral oophorectomy, all with surgery at least 1 month before dosing]).
27. For subjects who participate in the CSF substudy, the following exclusions apply:
 - A bleeding disorder that is not under adequate control (including a plate count $<50,000$, international normalized ratio [INR] >1.5 or partial thromboplastin time [PTT] $>$ upper limit of normal [ULN]).
 - Any contraindications to LP (eg, lower spinal malformation on physical examination, local spinal infection or other abnormality, or obesity to the extent that it makes LP technically difficult).

Study Treatment(s)

Study drug should be administered QD orally in the morning with or without food. Subjects will be instructed to take their other concomitant medications at the usual time.

Test drug: E2027

E2027 will be administered in size #2 hypromellose (HPMC) capsules containing 25 mg of E2027. Subjects randomly assigned to E2027 dose will take 2 × E2027 25 mg capsules.

Comparator Drug: E2027-matched placebo capsules

Subjects randomly assigned to placebo will take 2 × E2027-matched placebo capsules QD.

Duration of Treatment

All subjects will receive 12 weeks of treatment.

Concomitant Drug/Therapy

Prohibited and Restricted Concomitant Medications:

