9.4 Treatment(s)

9.4.1 Treatments Administered

The following treatments will be administered to subjects in this study ([Table 4](#)).

Table 4 Treatments Administered

Drug Name	Strength	Oral Dose Form	Number Dispensed and Frequency	Duration
E2027	25 mg	capsules	2 × 25 mg capsule QD	12 weeks
Placebo	N/A	E2027-matched capsules	2 × E2027-matched placebo capsule QD	12 weeks

N/A = not applicable, QD = once daily.

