## 5.2.3 Protocol Deviations

Major protocol deviations for the PP Analysis Set include:

- Subject did not meet Inclusion Criterion #2, which was: 2. Meet criteria for probable DLB (e.g. date of diagnosis of DLB missing).
- Subject met Exclusion Criteria #6, which was: 6. GDS score >8.

- Subject received incorrect study treatment for more than 6 weeks.
- Subject initiated prohibited medications used in the treatment of dementia during the 12 weeks treatment period.

Subject had poor compliance with study treatment (e.g., overall compliance is <80%).

In addition, subjects with treatment duration less than 6 weeks will be excluded from the PP Analysis Set.

The number (percentage) of subjects excluded from PP analysis will be summarized by reason for exclusion and treatment group. A listing of subjects excluded from PP analysis will be provided along with the description of reason for exclusion.

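### The compliance denominator is capped at 84 units, but the regimen is 168 capsules, so compliance over a full course is doubled and the 80% per-protocol cut-off acts at 40%

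*SAP*

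**What the plan says.** SAP section 5.2.6 (Treatment Compliance) defines percent compliance as the number of units dispensed less the number returned, over the number planned, times 100. It calls the units tablets and ends: "The maximum of planned total number of tablets to be taken will be 84". Results are displayed in bands with cut points at 50%, 80%, 100% and 120%.

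The protocol describes the study drug as capsules, two per dose. Section 9.4.1, Table 4, lists "2 × 25 mg capsule QD" for E2027 and the matching two-capsule regimen for placebo, each for 12 weeks. The synopsis agrees: "Subjects randomly assigned to E2027 dose will take 2 × E2027 25 mg capsules" and "Subjects randomly assigned to placebo will take 2 × E2027-matched placebo capsules QD". On duration it says: "All subjects will receive 12 weeks of treatment".

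SAP section 5.2.3 lists the deviations that remove a subject from the Per Protocol set. One reads "Subject had poor compliance with study treatment (e.g., overall compliance is <80" (per cent). A separate rule there states that "subjects with treatment duration less than 6 weeks will be excluded from the PP Analysis Set". In SAP section 5.4.1, Table 4, the Per Protocol set is used for a supplementary analysis of both co-primary endpoints, under both the non-EMA and the EMA methods.

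**The concern.** The numerator is a count of physical units handed out and not returned. The cap on the denominator equals the number of days in 12 weeks. With two capsules a day these are different scales, and the ratio for a full course is twice the true adherence.

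Two planned outputs suffer. The compliance table would put nearly every adherent subject in its top band, as if they had taken too much drug, and would show half-adherent subjects as perfect. The Per Protocol set would fail to remove most of the poorly compliant subjects it is meant to remove, so the supplementary analysis would not describe the effect in compliant subjects.

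**Working it through.** **Inputs**
- Capsules per day: 2 (Protocol synopsis and section 9.4.1, both arms)
- Duration: 12 weeks = 12 × 7 = 84 days (same places)
- Cap on planned units: 84 (SAP 5.2.6)
- Per-protocol cut-off: below 80% (SAP 5.2.3)
- Minimum treatment duration for the Per Protocol set: 6 weeks = 42 days (SAP 5.2.3)

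**Can 84 be reproduced?** Planned units = units per day × 7 × weeks.
- One unit per day: 1 × 7 × 12 = 84, which matches the SAP.
- Two units per day, as in the protocol: 2 × 7 × 12 = 168, which does not.

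So 84 is the count of dosing days or daily doses, not of capsules.

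**Full 12-week course.** Computed compliance = capsules taken / 84. True compliance = capsules taken / 168.

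| Capsules taken | True | Computed as written |
|---|---|---|
| 168 | 100% | 200% |
| 134.4 | 80% | 160% |
| 84 | 50% | 100% |
| 68 | 40.5% | 81.0% (kept) |
| 67 | 39.9% | 79.8% (excluded) |

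The cut-off falls at 0.80 × 84 = 67.2 capsules, and 67.2/168 = 40%.

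**Display bands.** Each cut point corresponds to half its nominal value, because 84/168 = 0.5. The cut points at 50%, 80%, 100% and 120% therefore act at true adherence of 25%, 40%, 50% and 60%. Everyone above 60% (1.20 × 84 = 100.8 capsules; 100.8/168) lands in the top band.

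**Subjects who stop early.** The SAP gives only the maximum and does not say how planned units are counted for a shorter course. Two readings for a subject treated D days (D from 42 to 84):

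| D (days) | Fully adherent score if planned = min(2D, 84) | True adherence at the 80% cut-off | Fully adherent score if planned = D | True adherence at the 80% cut-off |
|---|---|---|---|---|
| 42 | 100% | 80% | 200% | 40% |
| 56 | 133.3% | 60% | 200% | 40% |
| 63 | 150% | 53.3% | 200% | 40% |
| 70 | 166.7% | 48% | 200% | 40% |
| 84 | 200% | 40% | 200% | 40% |

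Under the first reading the score is 2D/84 and the cut-off is 67.2/(2D), so the same rule is stricter or looser depending on when the subject stopped. Under the second the distortion is constant.

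**After correction.** With a maximum of 168, full adherence gives 168/168 = 100%. The cut-off falls at 0.80 × 168 = 134.4 capsules: 134 (79.8%) is excluded and 135 (80.4%) is kept.

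**The case against.** The best defence is that a tablet in the SAP means one two-capsule daily dose. If drug accountability counted daily doses in both numerator and denominator, 84 would be right and only the wording would be at fault. Programming rules sit in separate documents (SAP section 9), so this cannot be ruled out. But nothing in the protocol or SAP defines such a unit, the product is supplied as capsules, and dispensed less returned is naturally a capsule count. The text needs correcting on either reading.

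Four further points have merit as limits on size:
- 84 is a maximum. Exact doubling and the 40% threshold hold for subjects treated the full 12 weeks, or for everyone only if planned units are counted at one per day.
- Subjects treated for less than 6 weeks leave the Per Protocol set under their own rule. The gap concerns poor intake among those treated longer.
- The 80% figure is introduced as an example and is one of several exclusion reasons. It is, however, the only compliance threshold given, and any threshold applied to this ratio would be distorted in the same way.
- Efficacy conclusions rest on the Full Analysis Set, and the per-protocol analyses are supplementary. This limits the consequence but does not make the rule correct.

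**Conclusion.** The concern holds. Followed literally, the formula gives 200% for perfect adherence over 12 weeks, and the poor-compliance exclusion acts at 40% instead of 80%. Full-course subjects who took from 68 to 134 of 168 capsules (40.5% to 79.8%) would stay in the Per Protocol set when the stated rule means to exclude them.

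This rests on units being counted as capsules and, for the exact factor of two, on a full-length course. Full-length courses should be the majority, given the 12% dropout assumed in the sample size section. The documents contain no adherence data, so the number of subjects wrongly kept cannot be estimated. The co-primary analyses on the Full Analysis Set are unaffected.

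**What to change.** In SAP section 5.2.6:
- Set the maximum planned number to 168 capsules (2 per day × 84 days).
- State that for subjects who stop early it is 2 × planned dosing days.
- Replace tablets with capsules throughout the section.

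Leave the 80% criterion in section 5.2.3 and the display bands unchanged; they work on the corrected scale. An equivalent alternative is to keep 84 and define the unit as a two-capsule daily dose in both numerator and denominator, with returned capsules converted accordingly. Whichever is chosen, the derivation specification should match.

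The cost is one number, one word and one sentence in the SAP, made before database lock. No new data are needed and the dosing is not touched. The Per Protocol set may become somewhat smaller.

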## 5.3 Data Analysis General Considerations

### 5.3.1 Pooling of Centers

This is a multi-center, international study conducted in three geographic regions, i.e. United States, Europe, and Japan. Sites will be pooled into the three regions, in order to have sufficient number of subjects per treatment group.

### 5.3.2 Adjustments for Covariates of Interest

The baseline value will be used as a covariate, and stratification variables (on AChEI or not and geographical region (US, Europe, Japan)) will be used as factors in the efficacy models

for analysis of continuous endpoints. Baseline for the primary and secondary efficacy endpoints is defined as the last pre-treatment assessment.

### 5.3.3 Multiple Comparisons/Multiplicity

There are 2 co-primary endpoints, change from baseline in the MoCA total score at 12 weeks and CIBIC-Plus score at 12 weeks. Overall there are 2 null hypotheses to be tested in the primary efficacy analysis. The study will be considered positive if statistically significant improvement (at level of 0.05 (2-sided) or 0.025 (1-sided)) is observed in both co-primary endpoints in E2027.

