8.2 Secondary Objectives

(Order of secondary objectives revised per Amendment 05)

- To determine whether E2027 is superior to placebo on the following secondary endpoints after 12 weeks of treatment:
 - Clinician Global Impression of Change in Dementia with Lewy Bodies (CGIC-DLB)
 - Cognitive Fluctuation Inventory (CFI)
 - Mini-Mental State Examination (MMSE)
 - Neuropsychiatric Inventory (NPI)
- To evaluate the safety and tolerability of E2027 in subjects with DLB
- To characterize the population pharmacokinetics (PPK) of E2027 in subjects with DLB, including evaluation of the effects of intrinsic and extrinsic factors on E2027 PK

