9.7.1.1.2 SECONDARY ENDPOINTS

(Order of secondary endpoints revised per Amendment 05)

- CGIC-DLB at 12 weeks of treatment
- Change from baseline at 12 weeks of treatment in the following endpoints:
 - CFI score
 - MMSE total score
 - NPI total score, subscores and caregiver distress score
- Safety and tolerability of E2027 as measured by (revised per Amendment 02):
 - Incidence of adverse events including severe AEs, serious AEs, AEs resulting in discontinuation (revised per Amendment 02)
 - Incidence of orthostatic hypotension and orthostatic tachycardia (revised per Amendment 02)
 - Incidence of markedly abnormal laboratory values and shifts from baseline of laboratory values (revised per Amendment 02)
 - Incidence of abnormal ECG parameters and abnormal ECG findings (revised per Amendment 02)
 - Incidence of suicidality based on C-SSRS (revised per Amendment 02)
 - Changes from baseline in the total score of UPDRS-III (revised per Amendment 02)

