9.7.1.6 Efficacy Analyses

The significance level for all efficacy endpoint analyses is 0.05 (2-sided), unless otherwise stated, with no adjustments for multiplicity. The efficacy analyses will be performed on the FAS except per protocol analysis will be performed on the PPS.

Baseline for the primary and secondary efficacy endpoints is defined as the last pretreatment assessment. An additional baseline, based on the mean of all prerandomization values at the Screening and Baseline assessment, will be explored due to assess potential prerandomization variability.

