##### 3.1.2 Secondary Objectives

1. To determine whether E2027 is superior to placebo on the following secondary endpoints after 12 weeks of treatment:
  - 1.1. Clinician Global Impression of Change in Dementia with Lewy Bodies (CGIC-DLB)
  - 1.2. Cognitive Fluctuation Inventory (CFI)
  - 1.3. Mini-Mental State Examination (MMSE)
  - 1.4. Neuropsychiatric Inventory (NPI)
2. To evaluate the safety and tolerability of E2027 in subjects with DLB
3. To characterize the population pharmacokinetics (PPK) of E2027 in subjects with DLB, including evaluation of the effects of intrinsic and extrinsic factors on E2027 PK

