#### **5.1.2 Secondary Endpoints**

CGIC-DLB scale at 12 weeks of treatment

- Change from baseline at 12 weeks of treatment in the following endpoints:

- CFI score
- MMSE total score
- NPI total score, subscores and caregiver or informant distress score

Safety and tolerability of E2027 as measured by

- Incidence of adverse events including severe AEs, serious AEs, AEs resulting in discontinuation
- Incidence of orthostatic hypotension and orthostatic tachycardia
- Incidence of markedly abnormal laboratory values and shifts from baseline of laboratory values
- Incidence of abnormal ECG parameters and abnormal ECG findings
- Incidence of suicidality based on C-SSRS
- Changes from baseline in the total score of UPDRS-III

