#### 5.4.2 Secondary Efficacy Analyses

Table 5 Secondary Efficacy Analyses			
Score		Analysis for non-EMA Registration	Analysis for EMA Registration
CGIC-DLB	Secondary analysis	GLMM	Proportional odds model with control-based pattern imputation
	Additional secondary analysis	Proportional odds model with control-based pattern imputation	GLMM
CFI	Secondary analysis	MMRM	Control based mean imputation with Mehrotra
	Additional secondary analysis	Control based mean imputation with Mehrotra	MMRM

MMSE	Secondary analysis	ANCOVA and multiple imputation (MI) assuming MAR	ANCOVA and control-based pattern imputation
NPI	Secondary analysis	MMRM	Control based mean imputation with Mehrotra
	Additional secondary analysis	Control based mean imputation with Mehrotra	MMRM
MoCA	Additional secondary analysis	Control based mean imputation with Mehrotra	MMRM
CIBIC-Plus	Additional secondary analysis	Proportional odds model with control-based pattern imputation	GLMM

Table 5 details the analyses for the secondary endpoints. Further details are described below.

The CGIC-DLB scale will be analyzed as ordinal response data in a manner similar to the primary analysis of co-primary endpoint based on CIBIC-Plus, according to both methods for non-EMA and EMA registrations.

CFI is a continuous variable and will be analyzed in a manner similar to the primary analysis of co-primary endpoint based on MoCA, according to both methods for non-EMA and EMA registrations.

For the non-EMA registration, MMSE will be analyzed using ANCOVA with MI assuming MAR. For the EMA registration, MMSE will be analyzed using ANCOVA with control-based pattern imputation at subject level for missing data handling (Yang Yuan, Paper SAS270-2014, SAS Institute Inc.). The ANCOVA model will include corresponding baseline as a covariate, with treatment group and randomization stratification variables as factors.

NPI will be analyzed in a manner similar to the primary analysis of co-primary endpoint based on MoCA, according to both methods for EMA, and non-EMA registrations.

The details of calculating all efficacy endpoints are presented in Section 8.3 ALGORITHMS FOR EFFICACY PARAMETERS.

Additional secondary efficacy analyses will be performed with or without inclusion of efficacy data collected after treatment discontinuation:

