### Neuropsychiatric Inventory (NPI)

This scale assesses frequency and severity of 12 neuropsychiatric symptoms commonly described in dementia patients: delusions, hallucinations, agitation/aggression, depression/dysphoria, anxiety, elation/euphoria, apathy/indifference, disinhibition, irritability/lability, motor disturbance, nighttime behaviors and appetite/eating changes. The scale is composed of 12 items, each item score ranges from 0 to 12.

The NPI Total Score (range 0 to 144) = sum of all item scores. If any item score is missing then the Total Score is missing. The higher the total score, the more severe the symptoms.

A subscore covering the domains of delusions, hallucinations, apathy and depression (NPI-4) will also be derived. The subscore (0 to 48) = sum of 4 corresponding item scores. If any one of the 4 item scores is missing then the subscore is missing.

The caregiver distress (NPI-D) is rated by caregiver based on his or her own stress on a five point scale from 0 - no distress, 1- minimal, 2 - mild, 3 - moderate, 4 - moderately severe, 5 - very severe or extreme.

NPI-10 is the subscore (0-120) of all items except night-time behavior and appetite/eating changes. If any one of the 10 item scores are missing then the subscore is missing.

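### The SAP's multiplicity section covers only the two co-primaries, so the four ordered secondary endpoints have per-test but no family-wise error control

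*SAP*

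**What the plan says.** **Objective and order.** Protocol 8.2 frames the secondaries as superiority questions: "To determine whether E2027 is superior to placebo on the following secondary endpoints after 12 weeks of treatment". It lists CGIC-DLB, CFI, MMSE and NPI. Protocol 9.7.1.1.2 keeps that order and marks it as chosen: "Order of secondary endpoints revised per Amendment 05". SAP 3.1.2 numbers the same four from 1.1 to 1.4.

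**Level.** Protocol 9.7.1.6 says "The significance level for all efficacy endpoint analyses is 0.05 (2-sided), unless otherwise stated, with no adjustments for multiplicity", and the Synopsis repeats it. SAP section 5 also sets every test at two-sided 5% by default.

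**Decision rule.** SAP 5.3.3 says "Overall there are 2 null hypotheses to be tested in the primary efficacy analysis" and calls the study positive only if both co-primaries show significant improvement. It does not mention the secondaries.

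**Secondary analyses.** SAP 5.4.2, its Table 5 and Protocol 9.7.1.6.2 give models and missing-data methods, separately for the non-EMA and EMA registrations in the SAP. They contain no gate, sequence or stopping rule.

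**NPI.** The endpoint bullet in SAP 5.1.2 reads "NPI total score, subscores and caregiver or informant distress score". SAP 5.4.2 says only "NPI will be analyzed in a manner similar to the primary analysis of co-primary endpoint" for MoCA, and points to section 8.3 for the calculation of endpoints.

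**The concern.** A list order is not a testing rule. Read literally, the plan lets any of the four secondaries be declared significant at 0.05, whatever the other three show and whether or not the co-primaries succeeded. Protocol 9.2 allows the study to be used as pivotal if both co-primaries are positive. That is the setting in which secondary superiority claims would be made, and in which a reader would ask how likely one of them is to be false. At present the plan offers only the per-test level in reply. A gate, a stopping point or an NPI score chosen after unblinding could not count as prespecified.

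**Working it through.** **Plan's own figure.** The documents state no family-wise error rate for the secondaries and no correlations between endpoints. What they give is the test level: 0.05 two-sided, so 0.05/2 = 0.025 in the favourable direction, critical value 1.96. That 0.025 is the benchmark.

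**Step 1. Four parallel tests, all four nulls true.** Assume equally correlated normal statistics with correlation ρ. At ρ = 0:

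1 − (1 − 0.025)^4 = 1 − 0.9037 = 9.6%.

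For ρ > 0, integrate over the shared component u:

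P(any) = 1 − ∫ φ(u) · Φ((1.96 − √ρ·u)/√(1 − ρ))^4 du.

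**Step 2. Fixed sequence.** With all four nulls true, a false claim requires a favourable result on the first endpoint, so the error is 2.5% at every ρ.

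**Step 3. Joint with positive co-primaries.** Secondary claims matter mainly beside a positive co-primary result. Multiply the integrand by the probability, given u, that each co-primary statistic exceeds 1.96, with mean 1.96 + Φ⁻¹(power). Power is assumed to be 90% for each, so the mean is 1.96 + 1.28 = 3.24.

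| Correlation (assumed) | 0 | 0.3 | 0.5 | 0.7 | 0.8 | 0.9 |
|---|---|---|---|---|---|---|
| Step 1: any false favourable, 4 parallel tests | 9.6% | 8.7% | 7.8% | 6.5% | 5.7% | 4.7% |
| Step 2: fixed sequence | 2.5% | 2.5% | 2.5% | 2.5% | 2.5% | 2.5% |
| Step 3: joint with both co-primaries, parallel | 7.8% | 8.4% | 7.7% | 6.5% | 5.7% | 4.7% |
| Step 3: joint, gate plus sequence | 2.0% | 2.4% | 2.5% | 2.5% | 2.5% | 2.5% |
| Step 3: joint, parallel, CGIC-DLB effect real (3 nulls) | 5.9% | 6.6% | 6.2% | 5.5% | 4.9% | 4.2% |

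**Step 4. Sensitivity to co-primary power.** SAP section 4 gives 80 completers per arm and a MoCA difference of 0.6 with SD 1.3:

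Φ((0.6/1.3)·√(80/2) − 1.96) = Φ(2.92 − 1.96) = 83%.

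Its later pairing, a difference of 1.4 with the blinded SD of 3, has almost the same standardised effect (1.4/3 = 0.467 against 0.6/1.3 = 0.462), so power is also above 80%. With MoCA power at 83% and CIBIC-Plus power still assumed to be 90%, the joint figure is 4.7% to 8.2% for parallel tests and 1.9% to 2.5% with gate and sequence. If both co-primaries are null, the joint figure is at most 1.4% for parallel tests and 1.1% with gate and sequence.

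**NPI, text against text.** SAP 8.3 introduces itself as deriving total scores for a list of scales that includes NPI. SAP 5.4.3 names MoCA and SCOPA-Sleep subscores where it wants them analysed, while SAP 5.4.2 names no NPI subscore. NPI total is therefore the natural reading. Against that, SAP 5.1.2 places total, subscores and distress in one bullet, and section 8.3 also defines scores that overlap the total, for example "NPI-10 is the subscore (0-120) of all items except night-time behavior and appetite/eating changes".

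**The case against.** **A stated choice.** This is a Phase 2 proof-of-concept study whose protocol openly declines multiplicity adjustment. Each secondary is still tested at 0.05. That stands against any reading that the secondaries have no error control at all: per-test error is controlled, and only family-wise control is absent. It does not remove the point, because the same protocol asks superiority questions of four endpoints and allows for pivotal use.

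**Evidence for a hierarchy.** The 1.1 to 1.4 numbering is weak evidence, since the exploratory objectives are numbered in the same way. The revision histories give a testing hierarchy as the purpose of the reordering, and a reader might infer that the protocol contradicts itself. It does not follow. Those entries are change history, and a fixed sequence that tests each endpoint at 0.05 is compatible with making no adjustment to the level. The point rests on the current text alone.

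**NPI.** A reader might infer that no NPI score is specified and count four NPI tests (total, NPI-4, NPI-10, distress), seven secondaries in all: 1 − 0.975^7 = 16.2% if independent. The text does not support that count. The total is the natural reading, and the scores overlap.

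**Size.** The joint figures assume that every secondary is null beside effective co-primaries. That is an unlikely pairing, because CGIC-DLB draws on all the efficacy endpoints and MMSE is a second cognition scale. This stands: with a real CGIC-DLB effect, the 90%/90% range falls from 4.7–8.4% to 4.2–6.6%, still above 2.5%.

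**Remedy.** In Protocol 9.7.1.6 the exception clause follows the significance level and precedes the multiplicity wording, so it does not clearly reach the latter. A change to the SAP alone could leave the protocol saying the opposite. Nor do the documents show that time remains. Protocol 9.7.1 says only that the SAP is finalised before lock and unblinding, and the SAP is already at version 4. Both objections stand and shape the fix.

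**Conclusion.** The gap is real and limited to secondary claims. Followed as written, the plan tests four secondaries at two-sided 0.05 with no gate, sequence or stopping rule. With all four nulls true, the chance of a false favourable finding is 4.7% to 9.6% for correlations from 0.9 to 0, against 2.5% in a fixed sequence. These figures rest on an assumed common correlation and normal test statistics; the joint figures also rest on assumed co-primary power.

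A reader might infer that the trial's main conclusion is at risk. It is not: both co-primaries must succeed, and no secondary test can alter that. NPI needs a clarification, since the intended score can be inferred but is not named as the tested one. This should be fixed, but it does not undermine the design.

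**What to change.** If the treatment code has not been broken, add to SAP 5.3.3:

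> If both co-primaries are significant at two-sided 0.05 in favour of E2027, test CGIC-DLB, CFI, MMSE and NPI total in that order, each at two-sided 0.05, stopping at the first endpoint not significant in favour of E2027. Each registration uses its own Secondary analysis row of Table 5 throughout. NPI subscores, distress and all other analyses are nominal.

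Three further steps:

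- State explicitly that a MoCA-only proof-of-concept result (Protocol 9.2) opens no formal secondary claim. The gate has that effect, so the sponsor should adopt it knowingly.
- Record the change in SAP section 7.
- Align the multiplicity sentences in the Protocol Synopsis and 9.7.1.6, or say in SAP section 7 that the SAP supersedes them.

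**Cost.** One SAP paragraph and a section 7 entry, with no change to co-primary alpha or sample size. If the protocol sentences are amended, Protocol 11.1 requires authority and ethics submission for amendments that affect scientific quality. The statistical price is that formal secondary claims stop at the first non-significant endpoint, and none can be made if either co-primary fails.
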